7. STUDY POPULATION

7.1. Selection and Discontinuation/Withdrawal of Subjects

All entry criteria, including test results, need to be confirmed at Screening and Day -1.

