Procedure	Screening		SIG-001 Administration				Follow-up ¹						
	Days -91 to -2		Pre-Op Day -1	Dosing Day 1	Clinic Day 2	Discharge Day 3	Year 1			Year 2	Years 3-5		
	Screening 1 45 Days	Screening 2 ^b / Rescreen 45 Days					Month 1 W1, 2, 4 (± 2d)	Month 2-6 W8, 12, 16, 24 (± 5d)	Month 9&12 W36, 52 (± 7d)	FVIII Assessment ^a W3 (± 2d) W6, 10, 20 (± 5d) W32, 44 (± 7d)	Every 3 months W65, 78, 91, 104 (± 14d)	Every 6 months (FVIII Assessment) ^a W117, 143, 169, 195, 221, 247 (± 14d)	Every 6 months (Office Visit) W130, 156, 182, 208, 234, 260 (± 14d)
FVIII activity (chromogenic & one-stage assay)	X			X (Local)	X (Local)	X (Local)	X	X	X	X	X	X	
FVIII inhibitors	X						X W2, W4 only	X	X	X		X	
Blood draw ^j	X						X	X	X	X		X	
FVIII usage ^f	X	X	X	X	X	X	← →						
Anaesthesia Evaluation	X												
Eligibility Review	X	X											
Distribution of patient diaries and training ^c	X	X	X										
Haem-A-QoL ^e	X						X W4 only	X W24 only	X W52 only	X W104 only		X W156, 208, 260 only	
EQ-5D ^e	X						X W4 only	X W24 only	X W52 only	X W104 only		X W156, 208, 260 only	
Physical Activity ^c							X W4 only	X W24 only	X W52 only	X W104 only		X W156, 208, 260 only	
Patient Diary ^c	←											→	
Hospital Check-in			X										
IP Administration				X									
FVIII prophylaxis for surgery				X	X	X	X						
Overnight Fasting			X										
Discharge						X							
Adverse events	←											→	

Abbreviations: AE=adverse event; ECG=electrocardiogram; ICF=informed consent form; PK=pharmacokinetics; VWF=von Willebrand Factor; MRI= Magnetic Resonance Imaging

PROTOCOL

Title: Safety and Efficacy of Encapsulated Allogeneic FVIII Cell Therapy in Haemophilia A

Study No. SIG-001-121

Notes for Table 2 (Schedule of Assessments):

[figure not shown]
- a) FVIII Assessment Visits may occur at the study site, the patient's home or another approved alternative location. In addition to the blood draw, FVIII usage, adverse events, including bleeding episodes, and concomitant medications will be discussed with the patient.

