- b) Screening Visit 2 / Rescreening applies only to patients who have been determined to be eligible for the study but do not receive SIG-001 within the original screening window. Those subjects will be asked to return to the clinic for Screening Visit 2 / Rescreening to repeat select screening assessments. Patients must receive SIG-001 within 90 days of the original screening date. Subjects who fail screening assessments at Screening Visit 2 / Rescreening can rescreen once under a new subject ID.
- c) Patients should lie down for at least 5 minutes before the ECG assessment is performed. ECG assessments should be performed before vital sign assessments if possible. If blood samples need to be collected first, the ECG and vitals should be performed at least 10 minutes after blood sample collection.
- d) Vital signs include temperature, respiratory rate, seated blood pressure (BP), and pulse. Seated BP will be recorded after the patient has been sitting for at least 5 minutes. Three BP measurements will be recorded at screening, and the average will be calculated for eligibility assessment. After screening, a single BP measurement is sufficient.
- e) Diary training and completion of the weekly diary should be initiated only after the patient has been confirmed to be eligible for the study. Patients may be brought back for a separate visit to be trained on how to complete the weekly diary.
- f) FVIII usage history collected during screening will be based on medical records and patient recollection. During the hospital stay, FVIII usage will be recorded by hospital staff; otherwise, FVIII usage will be recorded by the patient in the electronic patient diary.
- g) If historical records are available, F8 genotyping does not need to be conducted at Screening.

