7.4. Exclusion Criteria

Patients meeting any of the following exclusion criteria will be considered ineligible for participation and will not be enrolled in the study:

1. Morbid obesity defined as body mass index (BMI) ≥ 35
2. Current FVIII inhibitors (>0.6 NBU/mL) or prior Immune Tolerance Induction (ITI)
Note: Patients with a history of low and/or transient inhibitors require Sponsor review and approval.
3. History of allergic reaction or anaphylaxis to recombinant FVIII products, alginate (including seaweed and algae), barium and barium products (including barium contrast agents), and/or products containing foetal bovine serum (FBS)
4. Evidence of any bleeding disorder in addition to haemophilia A
5. Abnormal laboratory values, as follows:
 - a) Platelet count $<100 \times 10^9/L$
 - b) Creatinine ≥ 1.5 mg/dL
 - c) Haemoglobin <11 g/dL
 - d) Elevated levels (i.e. greater than $2 \times$ ULN of aspartate aminotransferase (AST), alanine aminotransferase (ALT), or total bilirubin)
Note: Patients with a known history of Gilbert's disease and bilirubin levels above ULN are not excluded.
6. Active infection with Hepatitis B or Hepatitis C virus, defined as a positive HBsAg, HBeAg, HBV DNA, or HCV RNA results, or currently managed with antiviral medications for Hepatitis B or C
7. Uncontrolled HIV infection, defined as CD4+ counts $\leq 200/\mu L$ or by a viral load of >200 copies/mL
8. Active alcoholism or drug addiction during the 12 months before the screening visit
9. Active malignancy or history of malignancy in the 5 years prior to study entry, exclusive of surgically removed non-melanoma skin cancer
10. Participation in another investigational medicine or device study within 90 days of screening or 5 investigational product half-lives, whichever is longer
11. Prior administration of a gene therapy product
12. Treatment with emicizumab less than 6 months prior to screening.
Note: Patients with emicizumab exposure may be eligible before 6 months of prior exposure if FVIII activity assessed by one-stage assay is back to pre-emicizumab treatment levels.
13. Unable to tolerate general anaesthesia required for the laparoscopic procedure
14. History of:
 - a) Abdominal adhesions due to prior large, median laparotomy(ies)
Note: Uncomplicated prior laparoscopic procedures are not exclusionary (e.g. cholecystectomy, laparoscopic appendectomy or diagnostic laparoscopy).
 - b) Septic peritonitis

PROTOCOL

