9. STUDY PLAN

9.1. Screening and Enrolment

9.1.1. Screening of Subjects

Following completion of the consenting process, patients will undergo screening assessments as described in the Schedule of Assessments (Table 2 Schedule of Assessments). Once eligibility is verified, the Investigator or site staff will work with the patient to schedule the SIG-001 placement procedure. If the laparoscopic procedure is scheduled outside of the original screening window, the patient will return to the clinic for Screening Visit 2 to repeat select screening assessments. The reason for completing Screening Visit 2 should be clearly documented. Patients must undergo SIG-001 placement within 90 days of consent.

PROTOCOL

Title: Safety and Efficacy of Encapsulated Allogeneic FVIII Cell Therapy in Haemophilia A
Study No. SIG-001-121

All screening evaluations must be completed and reviewed to confirm that potential subjects meet all eligibility criteria. Screening assessments may be completed over several screening visits. The Investigator will maintain a screening log to record details of all subjects screened and to confirm eligibility or record reasons for screening failure, as applicable.

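### The only pre-dose FVIII inhibitor test is at Screening 1, so the inhibitor baseline can be up to 90 days old at dosing, although the protocol makes Day -1 the visit for confirming entry results and taking baseline

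*Protocol*

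**What the plan says.** **Rule for Day -1.** Protocol Section 7.1: "All entry criteria, including test results, need to be confirmed at Screening and Day -1". Section 9.2.1 admits patients that day for baseline assessments and to confirm eligibility.

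**Inhibitors as an entry test.** Section 7.4, exclusion 2, covers "Current FVIII inhibitors (>0.6 NBU/mL) or prior Immune Tolerance Induction (ITI". Its note adds: "Patients with a history of low and/or transient inhibitors require Sponsor review and approval".

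**Schedule.** The inhibitor row of Table 2 (Section 2) begins "FVIII inhibitors X X W2, W4 only". Read against the column headers, the first mark is Screening 1 and the second is the Month 1 column, limited to Weeks 2 and 4. Screening 2/Rescreen, Day -1 and Days 1 to 3 are blank. Section 13.5.1 refers to Table 2 for the timing of inhibitor testing.

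**Time allowed before dosing.** Table 2, note b: "Patients must receive SIG-001 within 90 days of the original screening date". Section 9.1.1: "Patients must undergo SIG-001 placement within 90 days of consent". The note to Figure 1 gives a 45-day screening window, after which Screening 2 repeats selected assessments.

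**Use of the result.** Inhibitor titre is a secondary endpoint (Section 5.2.2), and the synopsis summarises its change from baseline. Section 13.6.2 takes the latest pre-product result as baseline for laboratory data. Section 6.6.2 gives inhibitor development with a persistent titre above 0.6 NBU/mL as an example of a DLT.

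**The concern.** The protocol treats Day -1 as the point where eligibility is settled and baseline is taken, but schedules no inhibitor assay there. A *current* inhibitor is then judged, and change from baseline measured, on a sample that may be weeks or months old. Patients may go on receiving FVIII in that interval.

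An inhibitor first seen at Week 2 or Week 4 could have arisen or recurred between Screening 1 and dosing, and nothing in the planned data would show it. Section 6.5.2 says the effect of SIG-001 on the inhibitor response in humans is unknown, so timing relative to dosing matters for interpretation. With 3 to 6 patients per cohort, one misclassified case is 1/6 = 17% to 1/3 = 33% of a cohort. A DLT stops dosing, and Section 6.6.2 requires a substantial amendment before restart.

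**Working it through.** **1. Is there another pre-dose inhibitor measurement?**
- Table 2 can show repeats: haematology and biochemistry are marked at Screening 1, Screening 2 and Day -1. Inhibitors are not.
- The row "Eligibility Review X X" has marks at the two screening visits and none on Day -1.
- The stored-plasma draw (Table 2, note j) is taken at Screening 1 and not again until after dosing, so the gap cannot be closed later from stored samples.
- The pre-procedure check in Section 9.2.2 uses FVIII recovery, or a normal aPTT plus a PK difference that may come from an earlier visit. Neither is a Bethesda assay.

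So there is one pre-dose inhibitor test, and its result is the only available baseline.

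**2. Age of that test at dosing.** There is no Day 0, so days from Day -a to Day b = a + b - 1.
- Protocol maximum: Day -90 to Day 1 = 90 + 1 - 1 = **90 days**, which reproduces the stated limit. The Table 2 header starts at Day -91, which would give 91.
- Without Screening 2: Day -45 to Day 1 = 45 + 1 - 1 = **45 days**.

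**3. Gap from last pre-dose to first post-dose test.** Section 9.2.4 sets Week 1 at Day 7, so Week 2 is Day 14. The window of 2 days either side gives Days 12 to 16.

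| Last pre-dose sample | To Day 12 | To Day 14 | To Day 16 |
|---|---|---|---|
| Day -90 | 101 | 103 | 105 |
| Day -45 | 56 | 58 | 60 |
| Day -1 (proposed) | 12 | 14 | 16 |

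**4. How likely is an event in the gap?** Section 12.3.4 says only that new inhibitors are rare after more than 150 exposure days; no incidence is given. The rates below are assumptions, and all 18 patients are given the full interval. With p = 1 - exp(-rate × days/365.25), the chance of at least one case is 1 - (1 - p)^18.

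| Assumed rate per 1000 patient-years | 45 days | 90 days |
|---|---|---|
| 1 | 0.2% | 0.4% |
| 5 | 1.1% | 2.2% |
| 10 | 2.2% | 4.3% |
| 50 | 10.5% | 19.9% |

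The last row is a deliberately high value. It marks the upper end of the range and is not an expectation.

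**The case against.** **Confirmed may mean reviewed.** Section 9.1.1 uses the verb for checking completed evaluations. If Section 7.1 required re-assay, VWF antigen and viral serology would also need repeating, and Table 2 marks those at screening only. This stands: a reader might infer a proven contradiction, but the text is ambiguous. On the review reading, however, Day -1 adds no inhibitor information and the baseline is just as old.

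**Ninety days is a worst case.** This stands. It applies only when dosing falls outside the 45-day window and the sample was taken at the start of screening.

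**A patient with an inhibitor at screening is excluded.** This stands for a titre above 0.6 NBU/mL that the test detects. The concern is an inhibitor that arises or recurs afterwards, or was missed. Section 6.5.3 describes eligible patients as having no past titres, but the note to exclusion 2 allows some to enter, so recurrence is possible.

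**Other safeguards exist.** The pre-procedure recovery or aPTT check and the local FVIII activity tests on Days 1 to 3 bear on a clinically important inhibitor, and Section 10.1.8 allows extra tests when clinically indicated. None need reveal a titre near 0.6 NBU/mL, and none supplies a baseline titre.

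**One case does not automatically stop the study.** This stands. A reader might infer that any titre above 0.6 NBU/mL at Week 2 or 4 is a DLT. Section 6.6.2 lists it under Grade III-IV toxicity judged possibly or probably related, and requires persistence.

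**Attribution stays confounded.** This also stands. Patients receive FVIII around surgery and until the Week 1 visit, so a Day -1 titre cannot assign a later inhibitor to SIG-001 rather than to that exposure. It can only separate what was detectable before dosing from what appeared after.

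**Conclusion.** The point holds as a weakness in the inhibitor baseline, together with unclear wording about Day -1. The single scheduled pre-dose titre can be up to 45 days old at dosing, or 90 when Screening 2 is used, and the interval to the first post-dose test can reach 101 to 105 days. This rests on the column alignment of Table 2 and on applying the laboratory baseline rule of Section 13.6.2 to inhibitor titres; with only one scheduled pre-dose value, any other rule would select the same sample.

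The chance of harm is small: 0.4% to 4.3% for at least one case among 18 patients over 90 days, at assumed rates of 1 to 10 per 1000 patient-years. The consequence of a case could be large, since it could count as a DLT if the grade, persistence and relatedness conditions are all met. The documents do not support saying that a case would halt the trial, or that Section 7.1 unambiguously orders a repeat assay. The change is worth making because it is cheap and the trial is first-in-human.

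**What to change.** 1. In Table 2, add an FVIII inhibitor sample on Day -1, drawn before the pre-procedure FVIII bolus, and name it as the baseline for the inhibitor endpoint.
2. Add the test at Screening 2/Rescreen, so that patients dosed outside the 45-day window have a more recent result available before dosing.
3. Reconcile Sections 7.1 and 9.2.1 with Table 2: say whether confirmed means repeated or reviewed, test by test, including the other entry tests done only at screening, and mark the Day -1 eligibility check in the table.

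**Cost.** One or two assays per patient, at most 2 × 18 = 36, at visits that already draw blood.

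**Limits.** The Day -1 result may arrive after dosing. It then fixes the baseline but cannot confirm eligibility, which is why the Screening 2 test and the wording change are also needed. It does not resolve confounding by perioperative FVIII.

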7.2. Number of Subjects

Up to 18 patients will be enrolled in the study to receive SIG-001, including up to 3 initial and 3 additional patients per cohort (6 total) in 3 separate dose cohorts.

7.3. Inclusion Criteria

Patients must meet all inclusion criteria to be eligible for participation in the study:

1. Males aged 18 years or older
2. Diagnosis of Haemophilia A as follows:
 - a) Severe ($< 1\%$ FVIII activity) receiving FVIII prophylaxis or on-demand treatment; or
 - b) Moderately-severe ($\geq 1\% - \leq 2\%$ FVIII activity) receiving FVIII prophylaxis
3. Greater than 150 exposure days to treatment with FVIII products
4. Fertile males (not surgically sterilized) who have sexual partners that are women of childbearing potential must be willing to use a barrier method of contraception (e.g. condoms) for at least 90 days post-SIG-001 administration
5. Normal levels of VWF antigen (≥ 50 IU/dL)

PROTOCOL

Title: Safety and Efficacy of Encapsulated Allogeneic FVIII Cell Therapy in Haemophilia A
Study No. SIG-001-121

6. Able and willing to provide informed consent
7. Willing to withdraw from FVIII prophylaxis during specified periods in the study

7.4. Exclusion Criteria

Patients meeting any of the following exclusion criteria will be considered ineligible for participation and will not be enrolled in the study:

1. Morbid obesity defined as body mass index (BMI) ≥ 35
2. Current FVIII inhibitors (>0.6 NBU/mL) or prior Immune Tolerance Induction (ITI)
Note: Patients with a history of low and/or transient inhibitors require Sponsor review and approval.
3. History of allergic reaction or anaphylaxis to recombinant FVIII products, alginate (including seaweed and algae), barium and barium products (including barium contrast agents), and/or products containing foetal bovine serum (FBS)
4. Evidence of any bleeding disorder in addition to haemophilia A
5. Abnormal laboratory values, as follows:
 - a) Platelet count $<100 \times 10^9/L$
 - b) Creatinine ≥ 1.5 mg/dL
 - c) Haemoglobin <11 g/dL
 - d) Elevated levels (i.e. greater than $2 \times$ ULN of aspartate aminotransferase (AST), alanine aminotransferase (ALT), or total bilirubin)
Note: Patients with a known history of Gilbert's disease and bilirubin levels above ULN are not excluded.
6. Active infection with Hepatitis B or Hepatitis C virus, defined as a positive HBsAg, HBeAg, HBV DNA, or HCV RNA results, or currently managed with antiviral medications for Hepatitis B or C
7. Uncontrolled HIV infection, defined as CD4+ counts $\leq 200/\mu L$ or by a viral load of >200 copies/mL
8. Active alcoholism or drug addiction during the 12 months before the screening visit
9. Active malignancy or history of malignancy in the 5 years prior to study entry, exclusive of surgically removed non-melanoma skin cancer
10. Participation in another investigational medicine or device study within 90 days of screening or 5 investigational product half-lives, whichever is longer
11. Prior administration of a gene therapy product
12. Treatment with emicizumab less than 6 months prior to screening.
Note: Patients with emicizumab exposure may be eligible before 6 months of prior exposure if FVIII activity assessed by one-stage assay is back to pre-emicizumab treatment levels.
13. Unable to tolerate general anaesthesia required for the laparoscopic procedure
14. History of:
 - a) Abdominal adhesions due to prior large, median laparotomy(ies)
Note: Uncomplicated prior laparoscopic procedures are not exclusionary (e.g. cholecystectomy, laparoscopic appendectomy or diagnostic laparoscopy).
 - b) Septic peritonitis

PROTOCOL

Title: Safety and Efficacy of Encapsulated Allogeneic FVIII Cell Therapy in Haemophilia A
Study No. SIG-001-121

- c) Intraperitoneal mesh
- d) Inflammatory Bowel Disease (IBD), including ulcerative colitis or Crohn's disease
- 15. Other comorbidities that in the opinion of the Investigator increase the risk of abdominal adhesions
- 16. Any disease or medical condition that in the Investigator's opinion is a contraindication for anaesthesia or the laparoscopic procedure (e.g. prior significant cardiovascular events)
- 17. In the Investigator's judgment, the patient is unlikely to complete all protocol-required study visits, procedures, or comply with the study requirements for participation

7.5. Permitted/Excluded Medications and Therapies

All prescription and over-the-counter medications taken by a patient for 30 days before Screening will be recorded on the designated eCRF. The Investigator may prescribe additional medications during the study as long as the prescribed medication is not prohibited by the protocol (Section 7.5.3). Any concomitant medications added or discontinued during the study should be recorded on the eCRF.

7.5.1. Permitted Medications and Therapies

Prior to the laparoscopic procedure, patients will receive a single dose of antibiotic (or a single dose of 2 different antibiotics), per the site's standard clinical practice.

Following the Week 1 visit, patients will be withdrawn from FVIII therapy per the Investigator's discretion. If FVIII therapy is continued after the Week 1 visit, the reason for continuation will be recorded.

On-demand FVIII use is allowed throughout the duration of the study for the treatment of bleeding episodes, perioperative management for surgery or other medical procedures, or preventative for vigorous physical activity. Each use of exogenous FVIII will be recorded and reported during the study.

7.5.2. Criteria for Re-Starting Prophylactic Therapy

Patients may restart prophylaxis if their FVIII level is <2% normal activity in two separate occasions done at least one week apart after 8 weeks following SIG-001 placement. If a patient needs to restart prophylaxis prior to Week 8, the Investigator should contact the Medical Monitor for approval.

7.5.3. Prohibited Medications and Therapies

Medications that increase the risk of bleeding or that are contraindicated for laparoscopic surgery per the site's standard of care will be prohibited. Examples may include use of aspirin or nonsteroidal anti-inflammatory drugs (NSAIDs) in the 5 days period prior to, and following SIG-001 administration.

Emicizumab is prohibited any time during the trial unless the patient has already met the criteria to restart prophylaxis.

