3.2. Treatment Background

Currently approved therapies for haemophilia A include a number of plasma-derived and recombinant human factor VIII replacement products and, more recently, non-factor therapies. Restoration of circulating FVIII to approximately 12% of normal levels has been shown to prevent most spontaneous joint bleeding episodes (den Uijl et al., 2011). FVIII replacement is administered as frequently as 1 to 3 times per week, but breakthrough bleeds and joint disease still occur due to suboptimal adherence, non-ideal factor kinetics, and FVIII inhibitor development (HEMLIBRA, 2017). More recently, a non-factor bispecific antibody (emicizumab) was also approved for the treatment of haemophilia A; potential risks include thrombotic microangiopathy, thrombotic events, and coagulation test interference (Aledort, 2019; Peters & Harris, 2018; Weyand & Pipe, 2019).

PROTOCOL

Title: Safety and Efficacy of Encapsulated Allogeneic FVIII Cell Therapy in Haemophilia A
Study No. SIG-001-121

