10.2.1. FVIII Activity

Throughout the study, FVIII activity levels will be assessed by one-stage and chromogenic assays performed by the central laboratory from samples obtained at regular intervals. Per the Investigator's discretion, exogenous FVIII use will be washed out for a minimum of 96 hours (4 days for standard half-life FVIII products) and at least 168 hours (7 days for prolonged half-life rFVIII products) to ensure that only FVIII secreted by SIG-001 is measured.

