13.5.2. Factor VIII Activity Levels

Factor VIII activity (as measured by one-stage and chromogenic assays) will be summarized separately using summary statistics for each scheduled assessment, by dose cohort and overall. Factor VIII activity will be correlated to SIG-001 dose received.

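### One-stage FVIII readings taken after a permitted emicizumab start would be summarised as SIG-001 activity, because neither the washout rule nor the analysis text sets them apart

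*Protocol*

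**What the plan says.** **Who may receive emicizumab.** Section 7.5.3: "Emicizumab is prohibited any time during the trial unless the patient has already met the criteria to restart prophylaxis". Section 7.5.2 sets the criteria: "Patients may restart prophylaxis if their FVIII level is <2% normal activity in two separate occasions done at least one week apart after 8 weeks". It adds a second route: "If a patient needs to restart prophylaxis prior to Week 8, the Investigator should contact the Medical Monitor for approval". The protocol does not say whether that earlier route also lifts the emicizumab ban.

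**How the protocol regards emicizumab and the assay.** Section 3.2, on emicizumab: "potential risks include thrombotic microangiopathy, thrombotic events, and coagulation test interference". Exclusion 12 in Section 7.4 bars treatment within 6 months of screening. It makes an exception only "if FVIII activity assessed by one-stage assay is back to pre-emicizumab treatment levels".

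**What is washed out before FVIII sampling.** Section 10.2.1: "exogenous FVIII use will be washed out for a minimum of 96 hours", or 168 hours for prolonged half-life products, at the Investigator's discretion. The stated purpose is to measure FVIII from SIG-001 alone. Section 9.3 gives the same periods. Neither section mentions emicizumab.

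**What is analysed.** Section 13.5.2: "Factor VIII activity (as measured by one-stage and chromogenic assays) will be summarized separately using summary statistics for each scheduled assessment". The next sentence plans a correlation of FVIII activity with dose and names no assay. Section 13.5 takes all data to the end of Year 1 into the key efficacy analyses.

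**The concern.** The protocol guards the one-stage assay against emicizumab at entry but not during follow-up. A patient who starts emicizumab stays on the FVIII sampling schedule. Full compliance with the exogenous FVIII washout would not remove the interference. The summary rule then takes the reading in as if it were SIG-001 activity.

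FVIII activity is a secondary endpoint, and Section 6.5.2 presents it as a surrogate for clinical benefit. Cohorts hold at most 6 patients, so one distorted value can move a cohort mean a long way. The distortion is not random, because emicizumab is open mainly to patients with readings below 2%. At stake are the cohort summaries of one-stage activity after Week 8 and, depending on the assay chosen, the dose correlation.

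**Working it through.** The study is descriptive and derives no sample size, so there is no planned figure to reproduce. The check has four steps.

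**1. Direction of the shift.** Inclusion criterion 2 admits patients with FVIII below 1%, or from 1% to 2%. The usual restart criterion requires readings below 2%. From such a level a reading can fall by less than 2 IU/dL, so any material shift is upward. The documents do not give its size.

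**2. Visits exposed.** Table 2 schedules these Year 1 post-dose FVIII visits, leaving aside the local samples on Days 1 to 3: Weeks 1, 2, 3, 4, 6, 8, 10, 12, 16, 20, 24, 32, 36, 44 and 52. That makes 15. Year 2 adds 4 and Years 3 to 5 add 6 FVIII assessment visits, so the total is 25.

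- If the Week 8 sample can be the first qualifying reading and Week 10 the second, Weeks 12, 16, 20, 24, 32, 36, 44 and 52 remain: 8 of 15 in Year 1, and 8 + 4 + 6 = 18 of 25 overall.
- If qualifying readings must come later than Week 8, they are Weeks 10 and 12. That leaves 7 of 15 in Year 1, and 17 of 25 overall.

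These are the most scheduled visits one patient could have affected, assuming emicizumab starts straight after the second qualifying scheduled visit.

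**3. Effect on a cohort mean (assumed readings).** Take three patients, each with a true level of 1 IU/dL, of whom *k* read *R* on emicizumab:

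mean = ((3 − *k*) × 1 + *k* × *R*) / 3

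| Assumed *R* (IU/dL) | *k* = 1 | *k* = 2 |
|---|---|---|
| 5 | 2.3 | 3.7 |
| 10 | 4.0 | 7.0 |
| 20 | 7.3 | 13.7 |
| 50 | 17.3 | 33.7 |

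The true mean is 1.0. Section 6.4 uses 5 IU/dL as its decision threshold for individual patients. It serves here only as a yardstick. For the mean to reach 5:

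- *k* = 1: (2 + *R*) / 3 = 5, so *R* = 13.
- *k* = 2: (1 + 2*R*) / 3 = 5, so *R* = 7.

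Both readings would lie within the 6% to 22% that Table 3 predicts for the lowest dose, so they would not look implausible.

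**4. Dropping the values is not a neutral repair.** Let the true levels be 1, 6 and 8, with mean 15 / 3 = 5.0. If the first patient is on emicizumab and is left out, the mean is (6 + 8) / 2 = 7.0. Leaving the patient out removes the lowest true value and biases the summary upward again.

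**The case against.** **This belongs in the SAP.** The handling of values after a concomitant therapy is usual SAP content, and Section 13.1 defers detail to that document. It can also be argued that the all-data wording in 13.5 sets a time window and does not rule on contaminated samples. This has weight, and the SAP could settle the analysis side. But the protocol is not merely silent: it states a sampling rule with a declared purpose, and a summary rule for every scheduled assessment. Following both exactly gives the wrong result, and 10.2.1 is protocol text that an SAP does not amend.

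**The protocol already offers protection.** Chromogenic activity is summarised separately, FVIII data are listed by patient, and concomitant medications are recorded throughout. With so few patients, a jump in one-stage readings after an emicizumab start could be seen. This partly stands. However, the protocol neither says that the chromogenic assay is unaffected nor lets it govern.

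**Stronger readings that a reader might infer.** The documents do not support the following:

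- That failures will appear as responders. No responder is defined, no responder analysis is planned, and the size of the interference is not given.
- That loss of expression will be hidden. By the usual route it is documented by two low readings before emicizumab starts. What is at risk is the later summaries.
- That only non-responders are affected. A patient who responds and later loses expression also qualifies, and the route before Week 8 has no FVIII threshold.
- That the dose correlation certainly includes these values. No assay or time point is named for it, so they could enter.

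**Conclusion.** The point holds as a defect in the stated sampling and summary rules. One-stage readings after an emicizumab start would be counted as SIG-001 activity in a secondary endpoint, mostly in patients whose expression has failed, and they could enter the dose correlation.

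The exposure follows from Table 2: 7 or 8 of 15 scheduled Year 1 post-dose visits for a patient who switches at the first opportunity, plus later years. The upward direction follows from the protocol's own eligibility and restart levels. The effect on a mean does not follow from the documents, because it depends on assumed readings and on patients choosing emicizumab among the options for restarting prophylaxis. The illustration shows only that in a cohort of three a modest false reading is enough.

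**What to change.** In Sections 10.2.1 and 13.5.2, state that:

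1. One-stage results from the first emicizumab dose onward are listed and flagged. They are not treated as SIG-001 activity in the summaries or the dose correlation.
2. The patient stays in the summary. From that date the chromogenic result is used if the central laboratory confirms that emicizumab does not affect it. Otherwise the last value before emicizumab is carried forward.
3. The number of patients so handled is reported for each cohort, with a sensitivity summary using all values as measured.
4. The assay used for the dose correlation is named.

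The FVIII-based decision rules in 6.4 (5 and 100 IU/dL) and 6.6.2 (150 IU/dL) name no assay. They should be reconciled with 7.5.3, since some of them refer to any patient or to earlier patients. Access to emicizumab is unchanged.

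The cost is wording and one flag, since medication dates are already collected. The downside is that some late one-stage values are replaced by a chromogenic or an assumed value. Carrying a value forward assumes no recovery of expression. For a patient who qualified by readings below 2%, if both the carried and the true level stay below 2 IU/dL, the error in a mean of three from that patient is less than 2 / 3 = 0.7 IU/dL.
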